7.5 DRUG EXPOSURE AND COMPLIANCE

Drug exposure and compliance will be performed on Safety Population. The number of days that study drug was taken and study drug compliance will be summarized by treatment group.

Duration of exposure will be defined as:

(Date of Last Drug Administration – Date of First Drug Administration + 1 day) / 7 days, rounded down to an integer.

The percent compliance for SB204 will be calculated as follows and presented as follows:

$\% \text{ Compliance} = (\text{Number of Doses Expected} - \text{Number of Doses Missed}) / (\text{Number of Doses Expected}) * 100$

Where the number of doses expected is the defined as the number of days from Baseline to the Week 12/ET visit. Subject's diaries will be reviewed at each visit to report the number of doses that were missed.

Percent compliance will be summarized by frequency count and percentage of subjects with compliance as defined in the SAP. Percent compliance will also be summarized as a continuous variable using descriptive statistics.

7.6 TOLERABILITY

Cutaneous tolerability assessments (erythema, scaling, dryness, pruritus, burning/stinging) will be summarized by visit from Baseline to Week 12/ET by treatment group. The proportion of subjects in each treatment group who shift scores from Baseline at each visit will also be summarized.

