All three co-primary outcomes must show superiority over vehicle (p-value \leq 0.05) in order for efficacy to be demonstrated; therefore no adjustments for multiplicity will be made.

Secondary Efficacy Analyses

Secondary efficacy outcomes include the percent change in inflammatory and non-inflammatory lesion counts at Week 12/ET, the median time to 35% improvement in inflammatory lesions, and the median time to a two or more grade improvement in IGA.

Analysis of the secondary efficacy outcomes will be adjusted for multiplicity using a hierarchical step-down procedure. These endpoints will be tested in the specified order with the rule that once a p-value exceeds 0.05, endpoints further down in the order are not statistically significant.

Tolerability Analyses

Cutaneous tolerability assessments (erythema, scaling, dryness, pruritus, burning/stinging) will be summarized from Baseline to Week 12/ET. Additionally, change from Baseline in tolerability assessments will be summarized at Weeks 2, 4, 8, and 12/ET.

Safety Analyses

Adverse Events

All AEs that occur during the study will be recorded and classified on the basis of Medical Dictionary for Regulatory Activities (MedDRA) terminology. Treatment-emergent AEs (TEAEs) are defined as AEs with an onset on or after the date of the first study drug dose. Adverse events noted prior to the first study drug administration that worsen after Baseline will also be reported as AEs and included in the summaries.

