2.2 STUDY OBJECTIVES

The primary objective of this study is to compare the efficacy, tolerability and safety of SB204 4% and Vehicle Gel once daily for 12 weeks in subjects with acne vulgaris.

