4.3 TOLERABILITY ASSESSMENTS

The evaluator will assess the subject's face at Baseline and each study visit. The cutaneous tolerability assessment for visits other than Baseline should be performed at least 30 minutes after study drug application. Cutaneous tolerability evaluations will include erythema, scaling, dryness, pruritus and burning/stinging. Pruritus and burning/stinging will be based on the subject's report for the previous 24 hours. Cutaneous tolerability endpoints will be reported as an AE if they reach severe and/or result in subject's discontinuation from the study. Subjects who develop intolerance to the product as defined by scores of 3 (severe) on two or more categories of tolerability

(erythema, scaling, dryness, pruritus, burning/stinging) shall be discontinued from the study. Cutaneous tolerability assessments will be performed according to the following scales:

Erythema

Score	Description
0-None	No evidence of erythema present
1-Mild	Slight pink coloration
2-Moderate	Definite redness
3-Severe	Marked erythema, bright red to dusky dark red in color

Scaling

Score	Description
0-None	No scaling
1-Mild	Fine scales present to limited areas of the face, barely perceptible
2-Moderate	Fine scale generalized to all areas of the face
3-Severe	Scaling and peeling of skin over all areas of the face

Dryness

Score	Description
0-None	No dryness
1-Mild	Slight but definite roughness
2-Moderate	Moderate roughness
3-Severe	Marked roughness

Pruritus

Score	Description
0-None	No itching
1-Mild	Slight itching, not very bothersome
2-Moderate	Moderate amount of itching, somewhat bothersome
3-Severe	Severe amount of itching, definite discomfort and sleep may be disturbed

Burning/Stinging

Score	Description
0-None	No burning/stinging
1-Mild	Slight warm, burning/stinging sensation; not very bothersome
2-Moderate	Definite warm, burning/stinging sensation that is somewhat bothersome
3-Severe	Hot, tingling/sensation that has caused definite discomfort and may have disturbed sleep

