6.7 DISCONTINUATION OF INDIVIDUAL SUBJECTS FROM THE STUDY

Subjects who develop intolerance to the product as defined by scores of 3 (severe) on 2 or more categories of tolerability (erythema, scaling, dryness, pruritus, burning/stinging) shall be discontinued from the study.

If a subject is determined to be pregnant prior to Week 12, the subject will be discontinued from the study but followed until term.

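### Section 7.6 summarises cutaneous tolerability only visit by visit, so mild and moderate reactions that do not lead to discontinuation are not counted per subject over the study

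*Protocol*

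**What the plan says.** - **Objective (Section 2.2):** "The primary objective of this study is to compare the efficacy, tolerability and safety of SB204 4% and Vehicle Gel".
- **Analysis (Section 7.6):** the five signs (erythema, scaling, dryness, pruritus, burning/stinging) "will be summarized by visit from Baseline to Week 12/ET by treatment group". In addition, "The proportion of subjects in each treatment group who shift scores from Baseline at each visit will also be summarized".
- **Analysis (Synopsis, Tolerability Analyses):** "change from Baseline in tolerability assessments will be summarized at Weeks 2, 4, 8, and 12/ET".
- **Route into adverse events (Section 4.3):** "Cutaneous tolerability endpoints will be reported as an AE if they reach severe"; a sign that leads to discontinuation is also reported as an AE.
- **Exit rule (Sections 4.3 and 6.7):** a subject is discontinued for "scores of 3 (severe) on 2 or more categories of tolerability".
- **AE tables (Section 7.7.1):** treatment-emergent AEs are tabulated by number of subjects, preferred term and severity. Each subject counts once at the highest severity, and AE discontinuations are listed.
- **Early leavers (Section 4.1.6; Table 1, note 3):** the Week 12/ET evaluations, which include tolerability, should be done at premature discontinuation.

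Neither Section 7.6 nor the synopsis names a worst post-Baseline score per subject or a between-arm estimate for tolerability.

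**The concern.** A tolerability comparison should tell the reader how many subjects in each arm had a reaction at some time during treatment, and how bad it became. If reactions come and go, different subjects may be affected at different visits. No single by-visit column then gives the number affected, and adding columns counts persistent reactions more than once.

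The protocol counts each subject once at worst severity for AEs, but only part of the tolerability data is sure to reach those tables. A score of 2 at Week 2 that has resolved by Week 4 appears in one column and need not appear anywhere else. At stake is a fair description of mild and moderate local reactions to SB204 against vehicle. No efficacy inference is affected.

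**Working it through.** The protocol states no tolerability rate by visit, so there is no planned figure to reproduce. The check sets the sections side by side and then bounds what by-visit tables can show.

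**1. What is counted per subject**

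| Reaction | By-visit tables (7.6) | Counted once per subject over the study |
|---|---|---|
| Score 3 on any sign | yes | yes, as an AE (4.3, 7.7.1) |
| Any score leading to discontinuation | yes | yes, as an AE and in the discontinuation list (4.3, 7.7.1) |
| Score 1 or 2, subject stays in | yes | only if also recorded as an AE; 4.3 does not require it |

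The gap is the last row.

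**2. What by-visit shares say about the share ever affected**

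Inputs: four post-Baseline visits (Weeks 2, 4, 8 and 12/ET, from Table 1) and an assumed share p above Baseline at every visit, with all subjects assessed each time. The share ever affected, E, satisfies

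p ≤ E ≤ 4p.

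The lower limit holds if the same subjects react at every visit, the upper if different subjects react each time. If visits were independent, E = 1 − (1 − p)^4.

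| Assumed p | Lower | Independent visits | Upper |
|---|---|---|---|
| 2% | 2% | 7.8% | 8% |
| 5% | 5% | 18.6% | 20% |
| 10% | 10% | 34.4% | 40% |

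Two arms with identical by-visit columns could therefore differ up to fourfold in subjects affected (20/5 = 4).

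**3. Who is in each column**

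- Weeks 4 and 8: subjects still in the study. Those who left earlier are absent, including those removed under Section 6.7.
- Week 12/ET: Day 84 scores together with scores taken at early exit. For example, if 5% of 650 (0.05 × 650 = 32.5, about 33 subjects) left under Section 6.7 and all had exit scores recorded here, this column would carry the full 5%. A subject who reacted at Week 2, stayed and recovered would appear in it as unaffected.

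**4. Illustration of the between-arm difference**

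Assumptions: 650 per arm (Section 7.8), 5% of SB204 and 1% of vehicle subjects ever affected, each seen at exactly one visit, spread evenly. The 5% borrows the order of magnitude of the application-site reactions in Section 1.5. The 1% and the spread are assumed.

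- Per subject: difference 4.0 points. SE = √(0.05 × 0.95/650 + 0.01 × 0.99/650) = 0.0094, and 1.96 × 0.94 = 1.84 points. 95% CI 2.2 to 5.8.
- One column: 5%/4 = 1.25% (about 8 subjects) against 1%/4 = 0.25%, difference 1.0 point. SE = √(0.0125 × 0.9875/650 + 0.0025 × 0.9975/650) = 0.0048, half-width 0.94 points. 95% CI 0.1 to 1.9.
- Opposite extreme: if every reaction lasted through all four visits, each column would show the full 5% and 1%, and nothing would be lost.

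Depending on persistence, a column would show between a quarter of the per-subject difference and all of it under these assumptions.

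**The case against.** The strongest reply is that this is reporting detail. Section 7.1 leaves data reporting to the SAP, which is not at hand, and Section 7.6 does not exclude a worst-score table. That keeps the weight low. It does not dispose of the point, because Section 7.6 and the synopsis do state a method, and that method is by visit. Where the protocol means to defer specifics it says so, as for the imputation options (7.4.1) and the compliance categories (7.5).

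Several stronger readings are tempting, and the protocol does not support them:

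- *That no planned table counts subjects who ever reacted.* Severe and discontinuing reactions are counted per subject in the treatment-emergent AE table.
- *That mild and moderate signs can never be AEs.* Section 4.3 does not say that only severe or discontinuing signs qualify. Section 6.1 defines AEs broadly, and Section 6.2 asks an open question at each visit and records what the subject reports. Some will be captured, but not systematically.
- *That any severe score forces exit.* The rule needs a score of 3 on at least two signs, so a subject severe on one may stay.
- *That all later columns describe only subjects who tolerated the gel.* This selection affects Weeks 4 and 8, and leavers who do not return. Exit scores belong to Week 12/ET.
- *That averaging lets improvement in many subjects hide reactions in a few.* The synopsis says change will be summarised and names no mean for tolerability. Section 7.6 uses the proportion who shift.
- *That the 5% in Section 1.5 measures the dilution.* It concerns reported application-site reactions in a previous study, which resolved after discontinuation of the product and by the end of that study. Section 1.5 discusses tolerability scores separately.

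A worst-score table would also miss the 5 to 10 minute flush described in Section 1.5 if it has faded by the time of scoring, which Section 4.3 sets at 30 minutes or more after application.

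**Conclusion.** The point holds and is minor. For an outcome that the primary objective says will be compared between arms, the stated summaries give no per-subject count of mild and moderate reactions that do not lead to discontinuation, and no between-arm estimate. By-visit columns cannot be converted into that count: 5% at each of four visits is compatible with 5% to 20% ever affected. That range assumes equal shares and complete assessment at all visits. The 5% against 1% example rests on assumed rates and an assumed pattern over visits, so it shows a mechanism and does not estimate the size in this trial. Nothing here bears on the efficacy analyses or on the discontinuation rule itself.

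**What to change.** In Section 7.6 and the synopsis, add as the main between-arm tolerability summary each subject's worst post-Baseline score for each of the five signs. Take it over all post-Baseline assessments including early termination, in SAF subjects with at least one such assessment. Report by arm the proportion with:

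- any increase from Baseline,
- a score of 2 or more,
- a score of 3,

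each with the between-arm difference and its 95% confidence interval. Keep the by-visit tables as supportive and show the number assessed at each visit. While editing, align the two places, since the synopsis describes change from Baseline and Section 7.6 describes shifts.

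The cost is a wording change and one more table, with no new data, visit or procedure. The downside for the sponsor is presentational: the number of subjects shown with a reaction will be at least as high as in any by-visit column.

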7.7 SAFETY

7.7.1 Adverse Events

All AEs that occur during the study will be recorded and classified on the basis of Medical Dictionary for Regulatory Activities (MedDRA) terminology. Treatment-emergent AEs (TEAEs) are defined as AEs with an onset on or after the date of the first study drug dose. Adverse events noted prior to the first study drug administration that worsen after Baseline will also be reported as TEAEs and included in the summaries.

All information pertaining to an AE noted during the study will be listed by subject, detailing verbatim term given by the Investigator or designee, preferred term, SOC, onset date, resolution date, severity, seriousness, action taken, outcome, and drug relatedness. The event onset will also be shown relative (in number of days) to date of first dose.

Treatment-emergent AEs will be summarized by treatment group, the number of subjects reporting a TEAE, SOC, preferred term, severity, relationship to study drug (causality), and seriousness. When summarizing AEs by severity and relationship, each subject will be counted only once, within a system organ class or a preferred term, by using the event with the highest severity and greatest relationship within each classification.

Serious AEs will be summarized by treatment group, severity, and relationship to study drug, and individual SAEs will be listed by subject. In addition, a list of subjects who prematurely discontinue from the study due to an AE will be provided.

7.7.2 Physical Examination

Any clinically significant changes from Baseline will be documented as an AE.

7.7.3 Vital Signs

Blood pressure and pulse will be summarized by treatment group from Baseline through Week 12/ET. Additionally, change from Baseline in vital signs will be summarized at Week 2, 4, 8, and 12/ET. Any clinically significant changes from Baseline will be documented as an AE.

7.7.4 Urine Pregnancy Tests

Urine pregnancy tests results for WOCBP will be presented in data listings by subject.

7.8 SAMPLE SIZE AND POWER CONSIDERATIONS

Approximately 1300 subjects will be randomized into the study in a 1:1 ratio (650 in each arm) at approximately 50 sites in North America. In the previous phase 2 study, the pooled vehicle IGA ‘success’ rate was 7.1% and the pooled SB204 IGA success rate was 13.4%. Using NQuery Advisor v7 (Statistical Solutions, Ltd) to estimate sample size and statistical power, based on a vehicle IGA success rate of 7% and a 6% difference for the SB204 arm, a sample size of 1294 was estimated to have at least 95% power for a two-sided test at the $\alpha=0.05$ level using the continuity corrected chi-square test.

The statistical power for detecting treatment differences in inflammatory or non-inflammatory lesions exceeds 99% once at least 256 subjects are treated in each group. This is based on the following assumptions:

- For inflammatory lesions: vehicle mean change = -7.6, SB204 mean change = -14.1, and a common standard deviation = 17.1
- For non-inflammatory lesions: vehicle mean change = -5.8, SB204 mean change = -11.3, and common standard deviation = 11.8

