4.1.6 Discontinuation/Withdrawal Procedures

A subject may voluntarily withdraw from study participation at any time. If the subject withdraws consent and discontinues from the study, the Investigator will attempt to determine the reason for discontinuation and record the reason in the subject's study records and in the study database. If a subject is withdrawn because of an AE, that AE should be indicated as the reason for withdrawal. In the event of early discontinuation, (i.e., prior to Week 12/Day 84 visit) and whenever possible, the subject should be asked to return to the study center to complete the Week 12/ET evaluations. Subjects who withdraw from the study will not be replaced.

If at any time during the study the Investigator determines that it is not in the best interest of the subject to continue, the subject will be discontinued from participation. The Investigator can discontinue a subject at any time if medically necessary. The Investigator may discontinue a subject's participation if the subject has failed to follow study procedures or to keep follow-up appointments. Appropriate documentation in the subject's study record and the study database regarding the reason for discontinuation must be completed.

All subjects who fail to return to the study center for the Week 12/ET visit will be contacted by telephone to determine the reason(s) why the subject failed to return for the necessary visit or elected to discontinue from the study. If a subject is unreachable by telephone after a minimum of two documented attempts (one attempt on two different days), a certified letter will be sent requesting that the subject contact the Investigator.

Reasons for an Investigator's withdrawal of a subject may include, but are not limited to, the following:

- Safety (e.g., severe adverse reactions, pregnancy);
- Lack of efficacy as determined by the Investigator;
- When the requirements of the protocol are not respected (e.g., significant issues with dosing compliance);
- When a concomitant medication or treatment likely to interfere with the results of the study is reported, or required, by the subject (the Investigator will decide, in consultation with Chiltern whether the subject is to be withdrawn);

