7.4.1 Primary Efficacy Analyses

There are three co-primary efficacy outcomes:

- change in inflammatory lesions counts at Week 12/ET
- change in non-inflammatory lesions counts at Week 12/ET and
- IGA success at Week 12/ET which is defined as an IGA score of clear (0) or almost clear (1) and ≥ 2 grades less than Baseline

All three co-primary outcomes must show superiority over vehicle ($p\text{-value} \leq 0.05$) in order for efficacy to be demonstrated; therefore no multiplicity adjustments will be made to the co-primary outcome analyses..

Prior to analysis of co-primary outcomes, missing post-Baseline lesion counts and IGA scores results at each visit will be imputed using a Markov chain Monte Carlo (MCMC) multiple imputation methodology. Separate multiple imputation (MI) procedures will be used for each outcome, using Statistical Analysis Software (SAS) procedure MI. Details of PROC MI and options used in the imputation procedures will be provided in a statistical analysis plan. ITT

subjects with only Baseline assessments will have the Baseline value carried forward across all visits.

The primary analyses of the co-primary efficacy endpoints will be performed in the ITT population where missing data have been imputed as described above. Additional analyses of the co-primary outcomes will be performed using the PP population. To assess the sensitivity of the primary efficacy results to imputation methods, each co-primary outcome will be analyzed as described above, but with missing data imputed by last observation carried forward (LOCF) and Baseline observation carried forward (BOCF) on the ITT population.

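### Protocol Section 7.8: the sample size of 1294, the 95% power and the continuity-corrected test do not fit together; 1294 matches the uncorrected chi-square test

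*Protocol*

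**What the plan says.** Protocol Section 7.8 (Sample Size and Power Considerations) gives every input of the IGA calculation in one sentence. The planning rates are "based on a vehicle IGA success rate of 7% and a 6% difference for the SB204 arm". The result is that "a sample size of 1294 was estimated to have at least 95% power for a two-sided test" at the 0.05 "level using the continuity corrected chi-square test". The software named is nQuery Advisor v7. The same section sets 1:1 randomization of about 1300 subjects, 650 per arm.

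As background, the section reports pooled Phase 2 IGA success rates of 7.1% on vehicle and 13.4% on SB204. For the two lesion-count outcomes it claims power above 99% once 256 subjects per group are treated.

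Section 7.4.1 sets the success rule: "All three co-primary outcomes must show superiority over vehicle". Section 4.1.6 adds that "Subjects who withdraw from the study will not be replaced".

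**The concern.** The sentence can be checked from its own contents, and the three things it asserts (an N, a power and a test) do not agree. A continuity correction always raises the sample size for given rates, alpha and power. An N that matches the uncorrected formula to the subject therefore cannot also give the stated power under the corrected test.

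The figure matters more than one outcome's power usually would. Efficacy requires all three co-primary outcomes to succeed, and the lesion counts have almost no chance of failing under the stated assumptions, so IGA success in effect limits the power of the trial. There is little slack: 1300 is only six subjects above 1294, Section 7.8 states no inflation for dropout, and withdrawn subjects are not replaced. Anyone who re-runs the sentence as written will get 1360 rather than 1294 and will have to ask which part is wrong.

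**Working it through.** **Inputs, all from Section 7.8.** p1 = 0.07; p2 = 0.07 + 0.06 = 0.13; difference d = 0.06; mean rate = 0.10; two-sided alpha 0.05 (z = 1.960); power 0.95 (z = 1.645); equal arms.

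**Step 1: reproduce the stated N.** Chi-square test without continuity correction, pooled variance under the null:

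n = [1.960 × √(2 × 0.10 × 0.90) + 1.645 × √(0.07 × 0.93 + 0.13 × 0.87)]² / 0.06²

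= [0.8315 + 0.6944]² / 0.0036 = 646.8

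This rounds up to 647 per arm, or 1294 in total, which is exactly the stated figure. Power at 647 per arm is 95.01%.

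**Step 2: apply the test that is named.** The usual continuity-corrected sample size starts from the unrounded n of Step 1:

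n_c = (n/4) × [1 + √(1 + 4/(n × d))]² = (646.8/4) × [1 + √(1 + 4/(646.8 × 0.06))]² = 679.7

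This rounds up to 680 per arm, or 1360 in total. It exceeds 1294 by 66 subjects (66/1294 = 5.1%).

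**Step 3: power of each test at the sizes in the protocol.** The correction amounts to subtracting 1/n from the difference:

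power = Φ{ [d − 1/n − 1.960 × √(2 × 0.10 × 0.90/n)] / √[(0.07 × 0.93 + 0.13 × 0.87)/n] }

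At n = 647: Φ{(0.06 − 0.00155 − 1.960 × 0.01668)/0.01660} = Φ(1.552) = 93.97%. Without the 1/n term the argument is 1.646, which gives 95.01%.

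| Per arm (total) | Uncorrected, formula | Uncorrected, exact | Corrected, formula | Corrected, exact |
|---|---|---|---|---|
| 647 (1294) | 95.01% | 95.35% | 93.97% | 94.30% |
| 650 (1300) | 95.09% | 95.43% | 94.07% | 94.40% |

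The exact columns sum the two binomial distributions over every outcome that each test rejects, so they do not depend on a sample-size formula. Both approaches put the corrected test below 95% at 1294 and at 1300.

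**Step 4: look for another reading that yields 1294 with the corrected test.**

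- Unpooled variance, uncorrected: 644 per arm, 1288 in total.
- One-sided 0.05, corrected: 1144 in total.
- Phase 2 rates (7.1% and 13.4%): 599.4, so 600 per arm (1200) uncorrected; 630.8, so 631 per arm (1262) corrected.

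None gives 1294. Only the uncorrected test at 7% and 13% does.

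**Step 5: the other co-primary outcomes.** The lesion claims reproduce. At 256 per arm, power is 99.02% for inflammatory lesions (difference 14.1 − 7.6 = 6.5, SD 17.1) and 99.95% for non-inflammatory lesions (difference 11.3 − 5.8 = 5.5, SD 11.8). At 650 per arm both exceed 99.99%.

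**The case against.** The arithmetic is not in dispute; the case on the other side concerns weight.

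- **The shortfall is small and rests on rounded inputs.** It is about one point of power. At the Phase 2 rates quoted in the same section, the corrected test has 95.5% power at 647 per arm and 95.6% at 650. At 647 per arm, a difference of 6.18 points from a 7% vehicle rate would restore 95%, and uncertainty about the true rates is far larger than 0.18 points. This stands as a statement about the design, which is not underpowered against the evidence the protocol cites. It does not rescue the sentence, which says the calculation used 7% and a 6-point difference; the Phase 2 rates do not lead to 1294 under either test.
- **The named test is used for planning only.** Section 7.4.1 bases the primary IGA analysis on multiply imputed data and does not commit to a continuity-corrected chi-square test. The label therefore cannot change a p-value. This stands.
- **Where the slip lies cannot be proved.** Without the nQuery output, the error could be in the name of the test or in the stated power. The exact match at 647 per arm makes a mislabelled test the likelier explanation, but the remedy should allow for both.
- **The protocol states no overall power for the three outcomes together.** That IGA power is in effect the trial's power is an inference. It follows from lesion power above 99.99% at 650 per arm.

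**Conclusion.** The concern holds. With the inputs in Section 7.8, 1294 is the sample size for 95% power with the uncorrected chi-square test. The continuity-corrected test that the section names has about 94% power at 1294 and at 1300, and would need 1360 for 95%. The stated N, power and test cannot all be right together.

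The weight is minor: roughly one percentage point of planning power on the co-primary outcome with the least of it. The result rests on 7% against 13%, two-sided 0.05, equal arms and no allowance for missing data. The standard formula and exact enumeration agree on it.

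**What to change.** Check the nQuery output, then amend one phrase in Section 7.8 in one of two ways:

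- **A. Name the test that gives 1294:** a sample size of 1294 (647 per arm) was estimated to have at least 95% power for a two-sided test at the 0.05 level using the chi-square test without continuity correction.
- **B. Keep the corrected test and restate the power:** a sample size of 1294 was estimated to have about 94% power for a two-sided test at the 0.05 level using the continuity-corrected chi-square test.

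Enrolment of about 1300 stays as it is under either wording, and nothing changes in endpoints, analysis or conduct. The cost is a text correction.

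### Section 7.8 claims at least 95% IGA power with no allowance for missing Week 12 scores: 1300 subjects leave a 0.46% margin under the uncorrected chi-square and none under the continuity-corrected test it names

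*Protocol*

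**What the plan says.** Section 7.8 of the protocol sizes the trial on IGA success, "based on a vehicle IGA success rate of 7% and a 6% difference for the SB204 arm". It reports that "a sample size of 1294 was estimated to have at least 95% power for a two-sided test" at the 0.05 level, "using the continuity corrected chi-square test". The planning rates come from phase 2, where "the pooled vehicle IGA ‘success’ rate was 7.1% and the pooled SB204 IGA success rate was 13.4" percent. The same section states: "Approximately 1300 subjects will be randomized into the study in a 1:1 ratio (650 in each arm"). It gives no expected dropout or missing-data rate.

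Section 4.1.6 adds: "Subjects who withdraw from the study will not be replaced". It asks subjects who stop early to return for the Week 12/ET evaluations where possible. Under section 7.4.1, "missing post-Baseline lesion counts and IGA scores results at each visit will be imputed using a Markov chain Monte Carlo (MCMC) multiple imputation methodology". ITT subjects with only Baseline data have Baseline carried forward. The ITT population (section 7.2.1) is everyone randomized and dispensed drug, and all three co-primary outcomes must reach significance.

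**The concern.** Only six subjects separate the 1294 in the calculation from the 1300 to be randomized. Sections 4.1.6 and 7.4.1 nevertheless expect withdrawals and missing scores. Imputation keeps all 1300 in the analysis but does not recreate information that was never collected. Carrying Baseline forward makes each Baseline-only subject an IGA failure, which narrows the difference between arms.

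The IGA endpoint sets the power of the whole trial. On the protocol's own lesion assumptions, power at 650 per arm exceeds 99.99% for each lesion count. Any shortfall on IGA is therefore close to a shortfall for the trial. What is at stake is whether the stated chance of missing the planned effect, at most 5%, is accurate.

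**Working it through.** **Inputs (section 7.8).** p1 = 0.07, p2 = 0.13, difference d = 0.06, mean rate 0.10, two-sided alpha 0.05 (z = 1.960), power 95% (z = 1.645), 1:1 allocation, 650 per arm randomized. Missing rates of 5%, 10% and 15%, equal in both arms, are assumptions.

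**Reproducing 1294.** For the uncorrected chi-square,

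n = [1.960 × √(2 × 0.10 × 0.90) + 1.645 × √(0.07 × 0.93 + 0.13 × 0.87)]² / 0.06²
= (0.8315 + 0.6944)² / 0.0036 = 646.8, so 647 per arm and 1294 in total. This is an exact match.

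**The test that 7.8 names.** The continuity correction gives

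n_c = (n/4) × [1 + √(1 + 4/(n d))]², which with n = 647 is 679.9, so 680 per arm and 1360 in total. The stated 1294 is therefore the uncorrected figure.

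**Power at 650 per arm with complete data.**
- Uncorrected: z = (0.06 × √650 − 0.8315) / √0.1782 = 1.654, giving 95.1%.
- Corrected: replace n by n − 2/d + 1/(n d²) = 650 − 33.3 + 0.4 = 617.1. Then z = 1.561, giving 94.1%.

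**Margin before power drops below 95%.**
- Uncorrected: (650 − 647)/650 = 0.46%.
- Corrected: none, because 650 is already below 680.

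**Power if missing scores are wholly lost,** with effective n = 650 × (1 − m):

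| Assumed missing m | Effective n per arm | Uncorrected | Corrected |
|---|---|---|---|
| 0% | 650 | 95.1% | 94.1% |
| 5% | 617.5 | 94.1% | 92.9% |
| 10% | 585 | 92.9% | 91.5% |
| 15% | 552.5 | 91.5% | 89.8% |

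Read down a column, attrition alone costs 1.0, 2.2 and 3.6 points (uncorrected) or 1.2, 2.6 and 4.3 points (corrected). The gap of about 1 point between the columns at 0% comes from the choice of test and not from missing data.

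**Variations.**
- Every missing score counted as a failure (both rates multiplied by 1 − m, n = 650): 94.0% / 92.7% at 5%, 92.6% / 91.2% at 10%, 91.0% / 89.3% at 15%.
- Half the missing information recovered from other visits (an assumption): 94.6% / 93.5% at 5%, 94.1% / 92.9% at 10%, 93.5% / 92.2% at 15%. The uncorrected margin then becomes about 1%.
- Exact binomial enumeration at 650 per arm: 95.4% / 94.4%. It gives 95.3% uncorrected at 646 per arm and 94.5% at 620. The exact margin for the uncorrected test is thus somewhat wider than 0.46% but under 5%.

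**Lesion counts at 650 per arm.** For inflammatory lesions, z = (6.5/17.1) × √325 − 1.96 = 4.9. For non-inflammatory lesions, z = (5.5/11.8) × √325 − 1.96 = 6.4. Both powers exceed 99.99%.

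**The case against.** The strongest objection is that a missing Week 12 score is not a lost subject in this plan. The endpoint is Week 12/ET, and early leavers are to be assessed at discontinuation. Remaining gaps are imputed with everyone kept in the ITT population. This stands in part: the table is near the worst case under missing at random. It does not remove the point. ET visits depend on the subject returning, and Baseline-only subjects offer no post-Baseline data to recover. Even with half the information recovered, 10% missing gives 94.1% / 92.9%.

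Second, 7.8 does not say how phase 2 dropouts were counted. If the 7.1% and 13.4% rates already include them under similar handling, 7% versus 13% already absorbs some or all of the attrition, and the discount double-counts it. The document cannot settle this.

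Third, the planned difference was rounded down. At 7.1% versus 13.4%, 650 per arm gives 96.4% / 95.6%, and the uncorrected test holds 95% down to 600 per arm, or 7.7% missing. That is real slack, but the claim in 7.8 is made at 7% and 6 points.

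A reader might infer that about 0.5% missing data is what takes power below 95% under either test. The document does not support that: the 0.46% margin belongs to the uncorrected test alone, and the corrected test is below 95% with nothing missing. A reader might also put the true miss chance at 7 to 10%, or the cost of attrition at up to 5 points. Those figures need 10 to 15% missing, a rate the protocol never gives, and the 5-point figure also adds about 1 point that belongs to the test mismatch.

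**Conclusion.** The point holds in limited form. The claim of at least 95% power has almost no margin under the uncorrected chi-square (95.1% at 650 per arm). Under the test that 7.8 names it is not met even with complete data (94.1%). No allowance for missing scores is stated and withdrawals are not replaced. At assumed missing rates of 5 to 15% with full loss of information, attrition alone costs about 1 to 4 points.

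The size rests on three things that the protocol leaves open: the missing rate, how much ET visits and imputation recover, and whether the phase 2 rates already count dropouts. The consequence is modest. With full loss, power stays at or above 90% until about 19% missing (uncorrected) or 14% (corrected). The trial is not underpowered in any serious sense; the stated figure is more favourable than the stated inputs support.

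**What to change.** Keep 1300 and revise section 7.8 in a few sentences:

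- Name the test to which the quoted power belongs. 1294 is the uncorrected figure; the corrected test needs about 1360 for 95%.
- State the expected Week 12 missing rate and its basis.
- Say whether the phase 2 rates of 7.1% and 13.4% count dropouts, and how.
- Replace the claim of at least 95% with the IGA power at the resulting effective size. If 10% of scores were missing and fully lost, this would read as about 93% (uncorrected) or 91 to 92% (corrected).

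The cost is a less favourable planning figure. No subjects are added, and neither the analysis nor the conduct of the trial changes.
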